If the TESE procedure is performed too early, it is possible that no or insufficient suitable sperm cells can be found. TESE is an invasive procedure that can have complications such as infection and bleeding, although the chances of these complications are low. However, complications may occur even without freezing sperm cells. Additionally, it should be noted that the patient is constantly reminded of their genitalia during the postoperative period, which can cause dysphoria. The procedure should be performed in a way that avoids permanent damage to the testes, ensuring that the process is reversible in case the patients choose their assigned gender at birth or if there is sufficient tissue available to assess the presence of sperm cells at the time of gonadectomy.

Puberty progresses differently in each individual. In some cases, secondary changes occur faster than sperm maturation, leading to high levels of mental distress due to dysphoria, which may cause patients to refrain from undergoing TESE. This period can also be stressful and uncertain for both the child and the parents. Therefore, it

| | |
|-------------------------|---|
| | 
is important to provide comprehensive counseling and multidisciplinary support throughout the process.
 
Currently, there are no ideal clinical non-invasive parameters to determine the optimal timing for TESE. To determine the appropriate moment for a successful TESE there is need to set up a cohort study of all transfeminine adolescents who are referred for TESE. This will enable us to make better predictions in the future and optimize our fertility counseling and care.
 
Furthermore, we intend to improve the counseling and support provided to both parents and the child by examining the experiences of the referred group throughout the entire process and reflecting on the experiences of the group that has undergone TESE.
 |
| Objective | 
When is the TESE process most successful by:
 
 1. Identifying clinical non-invasive parameters that indicate a high likelihood of finding mature sperm cells. 2. Evaluating the experience of the process for patients and parents to determine the potential physical and emotional burden of the TESE process and identifying factors that can reduce this burden to improve feasibility. |

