| Recruitment of participants | 
The participants who have already undergone TESE will be approached by the primary treating physician during their clinic visit or via telephone. The participant information will then be sent to them via email or mail. During the next physical appointment that the participant has at gender clinic, the consent form will be signed in the presence of the researcher.
 
If the referral has not yet been made, the primary treating physician will inform the participant about the study during the fertility counseling session and provide them with the participant information after the consultation. If a referral for TESE is desired, the primary treating physician will contact the participants and their parents by phone to confirm their interest in participation. A one-week
 |

| | |
|---|---|
| | consideration period will then begin. If participation is desired, the consent form will be signed during the next physical appointment in the presence of the researcher. If the participant has a long distance to travel to the gender clinic and does not have any upcoming physical appointments in the near future, the consent form will be sent by mail with a prepaid return envelope. |
| Intervention | The participant information will include a request for permission to use data from the medical records for scientific research purposes. For the second part of the research question, we will also inquire whether the participant and their parents are willing to complete a questionnaire at least once and up to three times, with each questionnaire taking a maximum of 10 to 15 minutes. Additionally, a minimum of 5 study participants who have undergone TESE will be asked to participate in an interview, as well as their parents. Similarly, a minimum of 5 study participants who are referred to the andrologist will also be invited to participate in an interview, along with their parents. The interviews will take place once at location or via video call if there is a long travel distance, and they will last a maximum of 1 hour. |

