| Standard care / Standard treatment | All adolescents are referred for fertility counseling before starting puberty suppressants. In this consultation, a counseling session takes place regarding fertility preservation. If the patient expresses a desire for preservation and is eligible for TESE (due to age/early puberty/incapacity to produce ejaculation), they are referred to the andrologist. An intake appointment is scheduled, after which the indication for TESE is confirmed. Currently, the indication is based on blood values (testosterone, LH, FSH) and an ultrasound to determine testicular volume. If the testicular volume or laboratory values are still insufficiently indicative of a successful TESE, the examination is repeated after 3 to 6 months or upon the patient's request if puberty progresses more rapidly and intensely than expected, thus tailored to the patient. The TESE procedure is performed in an outpatient setting under general anesthesia with local anesthesia, using microsurgery |

| | |
|-----------------------------|---|
| | techniques to obtain small pieces of testicular tissue, ensuring reversibility of the procedure. |
| Study parameters | 
Primary outcome measures:
 
Part 1:
 
Ultrasound-determined testicular volumes before TESE procedure, when this is not available, we will use the measurements of the Tanner stage at the time of the procedure, by the pediatric endocrinologist.
 
Laboratory values (testosterone, LH, FSH) shortest before the TESE procedure, including subsequent measurements, collected as part of routine clinical care for non-study purposes
 
Age at the time of TESE
 
Presence of spermatozoa
 
Number of cryopreserved straws
 
Quality of obtained sperm cells (concentration/motility)
 
Part 2:
 
Experience of the TESE procedure for the patient and parents
 
Experience of counseling for the patient and parents
 
Experience of any waiting period for the patient and parents
 
Feasibility for adolescents: Outcome of TESE after referral (whether the TESE procedure was carried out or not)
 |
| Study endpoints | 
Secondary outcome measures:
 
Progression of secondary sexual characteristics/virilization from the time of referral to the TESE procedure
 
Subgroup of patients who temporarily discontinued puberty suppressants
 |

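### Signing consent at the next physical visit, with a narrow mail exception, may keep some early leavers out of the feasibility denominator

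*Protocol*

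**What the plan says.** Under Study parameters, the primary outcome measures for Part 2 include "Feasibility for adolescents: Outcome of TESE after referral (whether the TESE procedure was carried out or not". The background states the intended cohort as a "cohort study of all transfeminine adolescents who are referred for TESE". Together these make all referred adolescents the denominator of feasibility.

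Recruitment of participants sets the prospective sequence:

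- Information comes before referral: "If the referral has not yet been made, the primary treating physician will inform the participant about the study during the fertility counseling session".
- A telephone call follows: "If a referral for TESE is desired, the primary treating physician will contact the participants and their parents by phone to confirm their interest".
- The family then has one week to consider.
- Signature comes last: "If participation is desired, the consent form will be signed during the next physical appointment in the presence of the researcher".
- The exception is for a participant who has a long way to travel and who "does not have any upcoming physical appointments in the near future, the consent form will be sent by mail with a prepaid return envelope". Both conditions must be met.

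The only other route described is for patients already treated: "The participants who have already undergone TESE will be approached by the primary treating physician during their clinic visit or via telephone". They sign at their next gender clinic appointment.

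Inclusion criteria admit patients who are referred or about to be referred, under the care of a gender clinic, and who either have not begun puberty suppression or have stopped it. They do not require the patient to stay on the path to TESE.

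**The concern.** Enrolment needs a signature at a visit that comes after the call and the consideration week. The outcome asks whether the adolescent went on to TESE. A referred adolescent who changes her mind before signing is a case where TESE was not carried out. If she is not enrolled, the numerator is untouched and the denominator shrinks.

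Two kinds of leaver could be missed:

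- One lives nearby and has no further physical visit, so neither in-person signing nor the mail exception reaches her.
- The other starts puberty suppression before signing and may then fail the inclusion criterion on suppression. The protocol does not say at what moment that criterion is judged.

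The background itself says that distress may lead patients to refrain from TESE, and Objective 2 is to find what would reduce the burden and improve feasibility. Early leavers are informative on both, so their loss would also thin the evidence on burden.

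**Working it through.** **No plan figure to reproduce.** Sample size gives 30-40 adolescents over 2 years. The protocol gives no rate of early leaving and no expected share reaching TESE. All rates below are assumptions, shown as ranges.

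**Inputs (assumed)**

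- d: share of referred adolescents who leave before signing, 5%, 10% or 20%.
- c: share having TESE among the rest, 50% to 90%.
- q: share of those leavers who are never enrolled, 0, 50% or 100%.

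**Formulas**

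- True feasibility = c(1 - d), since no leaver has TESE.
- Observed feasibility = c(1 - d) / (1 - qd), since the missed leavers drop out of the denominator.
- Overstatement = observed minus true. When q = 100% it reduces to c × d.

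**One case in persons.** Take 40 referred and d = 10%, so 4 leave. Of the other 36, half have TESE (c = 50%), which is 18.

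- True: 18/40 = 45.0%.
- Half the leavers missed: 18/38 = 47.4%, or +2.4 points.
- All missed: 18/36 = 50.0%, or +5.0 points.

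**Overstatement in percentage points, for c from 50% to 90%**

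| Leave before signing (d) | None missed | Half missed | All missed |
|---|---|---|---|
| 5% | 0 | 1.2 to 2.2 | 2.5 to 4.5 |
| 10% | 0 | 2.4 to 4.3 | 5 to 9 |
| 20% | 0 | 4.4 to 8.0 | 10 to 18 |

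Check of the extremes: at d = 20%, c = 90% and q = 50%, 0.72/0.90 = 80.0% against a true 72.0%, so +8.0. With q = 100%, 0.72/0.80 = 90.0%, so +18.0.

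**Scale.** The half-width of a 95% confidence interval, 1.96 × √(p(1 - p)/n), runs from 9.3 points (n = 40, p = 90%) to 17.9 points (n = 30, p = 50%). Apart from the upper end of the all-missed column, the possible bias is smaller than the sampling error. Unlike sampling error, it acts in one direction and is not visible in the enrolled data.

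**The case against.** A reader might infer that early leavers never enter and that feasibility is overstated as a matter of fact. The text does not carry that, for five reasons.

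1. The sequence starts when a referral is wanted, not after it has been made, and Inclusion criteria admit patients still awaiting referral. Consent may come before referral, and anyone who drops out before being referred is not in the denominator at all.
2. The visit at which consent is signed is not said to be an andrology or TESE visit. Someone who gives up TESE but remains under gender clinic care can sign at a later appointment, and a distant patient without one gets the form by post.
3. The stated reason for refraining is that physical changes outpace sperm maturation. That fits the 3 to 6 month waits between examinations, after the andrology intake. By then a physical visit has normally taken place, and many such leavers could already have signed.
4. Some losses work the other way. Already treated patients who live nearby and have no further appointments may also be unable to sign. All of them had TESE, so missing them lowers the observed share.
5. A gap of 7 to 17 points can be produced by assuming, for example, 28 TESE among 40 referred with 4-6 leavers all lost (28/36 = 77.8% and 28/34 = 82.4%, against 70.0%), or 20 among 30 with 3-6 lost (20/27 = 74.1% and 20/24 = 83.3%, against 66.7%). That requires 33-50% of the 12 non-completers, or 30-60% of the 10, to leave in this short interval and be unrecoverable. Nothing in the protocol supports that.

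Signing in the researcher's presence is also a defensible choice for minors and an intimate subject.

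These points limit the size and the certainty. They do not close the gap. A nearby leaver with no later visit still has no described way to consent, and a return visit does not help someone who has become ineligible by starting suppression.

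A separate and firmer source of upward bias is that the retrospective route approaches only patients who had TESE. If they make up a share s of the cohort, observed feasibility is s + (1 - s)c. With c = 70%, s = 25% gives 77.5% and s = 50% gives 85%. Wider access to consent would not cure that, but a referral-list denominator would if the list reaches back over the same period.

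**Conclusion.** The point holds as a possible bias in a primary Part 2 outcome, not as an established one. The direction is clear for the losses at issue: each referred adolescent without TESE who is missed before signing raises observed feasibility.

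The size cannot be derived from the protocol. With 5-20% leaving before signing and 50-90% TESE among the rest, it is about 1 to 8 points if half the leavers are missed, 2.5 to 18 if all are, and zero if none are. The lower part of that range is the more plausible, because many leavers would still attend a gender clinic visit or would leave only after a visit had taken place.

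The consent procedure is not an error in itself. The weakness is that nothing in the described procedure would show how many referred adolescents were missed.

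**What to change.** 1. Report feasibility with the clinic's referral list as denominator, as anonymous counts of adolescents referred, consented, and with TESE performed or not. Show the share among consented participants beside it, so that any difference can be seen. Keep the log from the start, because the counts may be hard to reconstruct later.
2. Once the consideration week is over, offer mailed or digital consent to every participant, whatever the travel distance or planned visits. Keep signing at a visit as an option.
3. State at what moment the inclusion criterion on puberty suppression is judged, so that it is clear whether someone who was eligible at referral and later began suppression can still be enrolled.

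The cost is a small amendment to the protocol and consent procedure, postage or an electronic form, and a simple running count. Some consents would not be signed face to face, which the protocol already accepts for distant participants. Clinical care is unchanged.

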To maximize the chances of a successful TESE, spermatogenesis should already be underway, for which the production of testosterone is crucial. However, testosterone is also responsible for (irreversible) virilization, such as deepening of the voice and facial hair growth. Therefore, it is highly burdensome for this group of patients to postpone puberty suppression in order to secure their fertility for the future, especially considering that active fertility desire does not exist at the start of puberty.

Currently, there is a lack of valid clinical factors to predict when spermatogenesis has sufficiently progressed in transfeminine adolescents. The intratesticular testosterone level is significantly higher than the peripheral blood testosterone level, and the blood testosterone value is not determinative of the intratesticular level. Ideally, a high intratesticular testosterone level would be beneficial for

sperm production, while maintaining the lowest possible peripheral testosterone level to minimize virilization.

In the current clinical practice, the child endocrinologist determines the Tanner stage before initiating puberty suppression, followed by fertility counseling with the gynecologist. If fertility preservation is desired afterward, a referral to the andrologist is made to assess the indication for TESE and determine the optimal timing for the procedure. In cases where ejaculation is not possible, the andrologist uses ultrasound measurements of testicular volume, serum testosterone, LH, and FSH levels to make this determination. Recent Australian research in transfeminine adolescents has shown that testicular volume appears to be the most predictive factor. This finding is based on a retrospective cohort study with a small sample size of N=31 (11).

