| Statistical analysis | 
The statistical program SPSS will be used for analyzing the observational cohort and questionnaires.
 
Descriptive analyses will be conducted to display the central tendency (mean, median, and mode) and variation (range and standard deviation) of the included sample.
 |

| | |
|--|---|
| | 
To demonstrate a statistically significant relationship between different variables and the observed outcomes, linear and multivariate regression analyses will be employed. If necessary, adjustments will be made for confounding factors.
 
The questionnaires will be sent via Castor and analyzed using SPSS.
 
The interviews will be transcribed verbatim. Transcripts will be coded using the MaxQDA software program, from which thematic analysis themes will be derived.
 |
| Burden for the participant | 
The interviews are conducted face-to-face or, in the case of long travel distances, through video consultations. The interviews last for a single session of 45-60 minutes. The questionnaires are sent online and take approximately 15 to 20 minutes to complete. The topics of fertility and the physical changes related to the TESE procedure discussed in the interviews can be considered intimate information. However, it is important to note that these topics are also routinely discussed by physicians and psychologists during clinical visits. Therefore, participants may find it relatively normal to discuss these topics with their healthcare providers. Nevertheless, participants have the option to select "I do not want to complete this questionnaire" for each questionnaire, in which case the questions will be removed from the digital survey. Apart from the time invested in completing the questionnaires and/or participating in interviews, there is no additional burden on the participants. Blood tests are always part of the treatment process and there are no additional blood sampling moments.
 |
| Risk for the participant | The participant faces no risks. |
| Benefits of participating in the research | The participant does not have direct benefits from participating in the research. Indirect benefits may include the potential improvement of care and information provision within the Knowledge and Care Center for Gender Dysphoria, both nationally and internationally, based on the research outcomes. This can be perceived as highly meaningful. |

| | |
|---|---|

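### Does timing TESE on the same volume and hormone values that Part 1 tests as predictors call for a change to the plan?

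*Protocol*

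**What the plan says.** The background and the Standard care section agree on how TESE is timed. In the background, when ejaculation is not possible, "the andrologist uses ultrasound measurements of testicular volume, serum testosterone, LH, and FSH levels to make this determination". Standard care says the same: "Currently, the indication is based on blood values (testosterone, LH, FSH) and an ultrasound to determine testicular volume". It adds what happens when the values fall short: "If the testicular volume or laboratory values are still insufficiently indicative of a successful TESE, the examination is repeated after 3 to 6 months", or sooner if the patient asks. It gives no numerical threshold and says the approach is adapted to the individual.

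Under Study parameters, Part 1 lists ultrasound volume before TESE (Tanner stage if that is missing), age at TESE, and "Laboratory values (testosterone, LH, FSH) shortest before the TESE procedure, including subsequent measurements, collected as part of routine clinical care for non-study purposes". Beside them stand presence of spermatozoa, number of straws and sperm quality.

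The Statistical analysis section says: "To demonstrate a statistically significant relationship between different variables and the observed outcomes, linear and multivariate regression analyses will be employed". It also plans descriptive summaries of the sample and, if needed, adjustment for confounding.

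The background gives the motive: "To determine the appropriate moment for a successful TESE there is need to set up a cohort study" of all those referred, and "This will enable us to make better predictions in the future and optimize our fertility counseling and care". The Sample size section aims for 30-40 adolescents over 2 years, with no power statement.

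**The concern.** The variables that decide who is operated on, and when, are the candidate predictors. No sperm outcome exists at an examination that led to deferral. Three consequences are plausible:

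- The range of volume and hormones among those operated on is narrower than among those referred, which lowers discrimination and power.
- A predictor analysed alone can look weaker than it is, because selection on several values at once distorts their joint distribution.
- Success at values where TESE is usually deferred can only be extrapolated.

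The background worries about exactly that end of the scale: "If the TESE procedure is performed too early, it is possible that no or insufficient suitable sperm cells can be found". No sentence limits the aim to the values at which TESE was done. Results might then be used to counsel families about earlier TESE with little or no supporting data, or a non-significant coefficient in a small cohort might be taken to mean that a measure has no predictive use.

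**Working it through.** **1. Is there a figure to reproduce?** No. The 30-40 target comes without alpha, power, effect size or success rate.

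**2. Overlap.** Indication: testosterone, LH, FSH, ultrasound volume. Part 1 predictors: the same four, plus age. The overlap is confirmed.

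**3. Does it bias the regression?** If the decision to operate depends only on measured values X that are in the model, then P(sperm | X, operated) = P(sperm | X). A correctly specified joint logistic slope is therefore unchanged. Simulation agrees: the fitted volume slope stays at 0.30 under every selection rule tried.

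The second simulation used two standardised predictors with true slopes 0.90, correlation 0.3-0.7, and selection of 0.5, 1 or 2 log-odds per SD of each. The joint slopes stay near 0.90. Single-predictor log-odds fall by 2-4%, 8-12% and 17-27% respectively.

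**4. How much information could be lost?** All inputs here are assumptions, none is in the protocol, and no mL value is a proposed rule. Volume has mean 12 mL and SD 4.5. P(sperm) = expit(0.3 × (volume − m)) with m = 12 or 10. P(operated) = expit(k × (volume − c)) with c = 8 or 10. Power is for the two-sided 5% test of the volume-success correlation at n=30. Unselected power is 83-84%.

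| m | c | k=0.2 | k=0.3 | k=0.5 | k=0.8 | k=1.0 |
|---|---|---|---|---|---|---|
| 12 | 8 | 80% | 77% | 73% | 69% | 68% |
| 12 | 10 | 79% | 75% | 66% | 60% | 57% |
| 10 | 8 | 77% | 71% | 64% | 59% | 58% |
| 10 | 10 | 75% | 69% | 59% | 49% | 45% |

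- The gentlest selection costs about 3 to 9 points (83 − 80 to 84 − 75). The steepest costs about 15 to 39 (83 − 68 to 84 − 45).
- At n=40, power is 93-94% unselected and 91% to 58% selected.
- AUC goes from 0.79 to between 0.78 and 0.73.
- Volumes below 8 mL make up 18% of those referred and 11% to 1% of those operated on. In 30 operations that is 0.11 × 30 ≈ 3 down to 0.01 × 30 ≈ 0.
- With c = 10 and k from 0.2 to 1.0, the median 95% interval for predicted success at 6 mL widens from 43 to 49-63 points (m = 12) or from 51 to 60-75 (m = 10). At 12 mL it stays at 39-43.

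**5. A second model.** A standard normal index X has logit P(sperm) = 1.5X, and power = Φ(atanh(r)√(n−3) − 1.96) at n=30; differences in the last digit come from rounding r.

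- No selection: r = 0.53, power 0.86, AUC 0.81.
- Top half on the index itself: r = 0.29, power 0.35, AUC 0.70.
- Top half on an index correlated 0.7 with X: r = 0.45, power 0.72, AUC 0.78.

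The direction is the same, and the size again depends almost wholly on how strict selection is.

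**6. What these figures leave out.** They treat all 30-40 adolescents as operated on, whereas the inclusion criteria admit everyone referred or about to be referred. The unselected reference is also unattainable in a study of routine records.

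**7. Does the text claim more than the data can give?** The Objective asks when TESE is most successful, and Study design asks about sperm yield from TESE. The Part 1 measures are taken before, or at, a procedure that happened. No AUC, cut-off or prediction at deferred values is planned, and nothing says that non-significance will be read as no predictive value.

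**The case for a change.** The best case for a change is that the broad aim sits in the protocol itself, so its limit should too. A cohort of all referred adolescents is presented as the way to find the right moment, yet Part 1 can use only those judged ready. Adjustment for confounding cannot supply outcomes that were never observed. The remedy would cost only wording and one table, and would leave the clinical indication alone.

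Part of this stands. Success at values where TESE is usually deferred will be seen rarely or not at all, and the report should say so. Single-predictor results describe the operated group. Non-significance in a cohort this small is weak evidence of no association.

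It still does not amount to a fault in the plan. The broad phrasing is motivating background, while the objective and the Part 1 variables are already conditional on TESE. The remark about operating too early describes procedures that were done and yielded too little sperm; those failures are Part 1 outcomes, not missing data. Referred patients are already eligible, whether TESE went ahead is already recorded under Part 2, routine values are already collected, and descriptive summaries are already planned. Splitting those summaries by operated and non-operated status needs no new design or data.

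**Conclusion.** No change to the plan is needed. The overlap between indication and predictors is a fact of observing routine care, and an observational study cannot remove it. It leaves a correctly specified joint slope unbiased, provided selection acts through the values in the model. It contradicts nothing in the protocol, and no estimate or stated rule would differ if it were spelled out.

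Its cost in precision may be small or substantial. In the volume illustration, power at n=30 lies anywhere from 80% to 45%, and those two ends come from different assumed scenarios. With no stated threshold and decisions adapted to the individual, the protocol does not show where in that range the study would fall, and added wording would recover none of the loss.

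The limitation statement, the comparison of operated with deferred or non-operated examinations, and cautious reading of non-significant results are matters that analysts ordinarily settle in the SAP or the report. The SAP is not at hand, so their absence from the protocol is not a finding.

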| Study design | 
For part 1 of the research question "when is the sperm yield from TESE most successful," the study design is observational, including both retrospective and prospective cohort research, utilizing data from medical records.
 
To address the second part of the research question, we intend to employ a descriptive research method. This will involve qualitative research through interviews and quantitative research through questionnaires administered to both the children and their parents during or after the treatment.
 |
| Study population | 
Healthy adolescents assigned male at birth with gender dysphoria and a desire for surgical fertility preservation prior to or after the
 |

| | |
|------------------------------------|--|
| | temporary discontinuation of puberty suppression, who have been referred to the andrologist |
| Inclusion criteria | 
Patients will be included if they meet the following criteria:
 
 • (Parents of) Individuals assigned male at birth who identify as transfeminine (trans girl, non-binary person, etc.). • Under the care of a specialized gender center or clinic • Have a diagnosis of gender dysphoria according to the Diagnostic and Statistical Manual of Mental Disorders, Fifth Edition (DSM-5) or a diagnosis of gender incongruence according to the International Classification of Diseases, 11th Revision (ICD-11). • Have not yet started or have discontinued puberty suppression before the start of gender affirming hormone treatment. • Referred or scheduled for referral to the andrologist following fertility counseling. |
| Exclusion criteria | Patients will be excluded if they do not wish to participate in this research. |
| Sample size | We aim to conduct the study over a period of 2 years to include a sufficient number of 30-40 adolescents, allowing us to generate valid data. |

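### Part 1 lists five candidate predictors as primary outcome measures and does not fix which of three sperm results is the main one

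*Protocol*

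**What the plan says.** The Study parameters row of the Protocol gives one undivided list of primary outcome measures for Part 1. It opens with "Ultrasound-determined testicular volumes before TESE procedure, when this is not available, we will use the measurements of the Tanner stage", continues with testosterone, LH and FSH, and then has "Age at the time of TESE". The same list goes on to "Presence of spermatozoa", "Number of cryopreserved straws" and "Quality of obtained sperm cells (concentration/motility". Nothing separates predictors from results, and nothing is ranked. The secondary measures in the Study endpoints row are virilization between referral and TESE and a subgroup who paused puberty suppression. They take up none of the sperm results, so all of those remain primary.

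The target of Part 1 is worded in more than one way:

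- Objective 1 is "Identifying clinical non-invasive parameters that indicate a high likelihood of finding mature sperm cells".
- The Study design row states the Part 1 question as "when is the sperm yield from TESE most successful".
- The background, on a procedure done too early, says that "it is possible that no or insufficient suitable sperm cells can be found".

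The Statistical analysis row aims to show statistically significant relationships between variables and outcomes by linear and multivariate regression. It does not say which variables or which outcome.

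**The concern.** A list of primary outcomes should tell the reader what result the study will be judged on. This one mixes what is known before or at the procedure with what the procedure produces, and leaves three results on an equal footing. As labelled, an association between FSH and motility in the patients with sperm would count as a primary finding, level with an association between testicular volume and finding any sperm.

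This matters more than usual here because part of the cohort is retrospective. The Recruitment of participants row provides for people who have already had TESE, and their results are in the medical records before any analysis starts. Naming the main result in advance is then the chief protection against picking it afterwards. The background says the findings are meant to improve prediction and fertility counselling, so families and clinicians will rely on knowing which result was the question.

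**Working it through.** The protocol gives no figure to reproduce on this point. The check is a classification of the listed items and a side-by-side reading of the rows.

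**Step 1: what each listed item is.** Inputs: the Part 1 list in Study parameters, read against Objective 1, which looks for non-invasive parameters that foretell sperm retrieval.

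| Listed item | Role under Objective 1 |
|---|---|
| Testicular volume, or Tanner stage if volume is missing | predictor |
| Testosterone | predictor |
| LH | predictor |
| FSH | predictor |
| Age at TESE | predictor |
| Presence of spermatozoa | result (yes/no) |
| Number of straws | result (count) |
| Quality (concentration and motility) | result (two measures) |

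Count: 5 predictors + 3 results = 8 items, so the label is wrong for 5 of 8. Age at TESE makes this plainest, since it cannot be an outcome of TESE. Three results is a minimum: with concentration and motility counted separately there are four.

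**Step 2: does another row name the main result?**

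| Row | Which result it points to |
|---|---|
| Objective 1 | presence of mature sperm |
| Study design | yield, which suggests quantity |
| Background on early TESE | presence, amount and suitability |
| Study parameters | all three, unranked |
| Statistical analysis | outcomes in general, none named |

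Objective 1 leans to presence. No row designates it, and a successful TESE is nowhere defined.

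**Step 3: whom each result covers.** Enrolment is at referral or planned referral, and Part 2 counts whether TESE was carried out as an outcome of its own. So:

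- enrolled ≥ those who undergo TESE ≥ those with sperm found;
- presence is defined for everyone who undergoes TESE;
- quality of obtained sperm is defined only where sperm are found.

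The choice of main result therefore also changes the patients analysed. The protocol gives no retrieval rate, so the size of the smaller group cannot be stated.

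**Step 4: does the planned model fit?** Presence is a yes/no result. The Statistical analysis row names linear and multivariate regression, and neither term clearly provides a binary-outcome model. If presence is made primary, that row has to change too.

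**The case against.** The strongest reply is that this is a labelling slip. The row title, Study parameters, is broad; Objective 1 assigns the roles; the Statistical analysis row itself distinguishes variables from outcomes; and nobody would analyse age as a result of surgery. That is fair for the predictors, and it limits the damage from the label. It does not settle which of the three results is the main one.

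A second reply is that the two target wordings do not conflict. Yield restates the umbrella question of when TESE is most successful, Objective 1 makes it operational, and finding and freezing sperm are steps of one process. This also largely stands. A reader might infer a flat contradiction, or that any predictor-result pair could equally be presented as primary. The documents support less: a natural primary result exists but is not designated.

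Third, a reader might infer an inflated false-positive rate. With 5 predictors and 3 results there are 5 × 3 = 15 pairs, and 1 − 0.95^15 = 53.7%. That figure should carry no weight. It assumes a 0.05 level, one independent test per pair and no true association anywhere. The protocol states no level, plans regression rather than 15 separate tests, and itself describes testosterone production as crucial to sperm formation. Screening several parameters is the stated aim.

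Fourth, the SAP is not at hand and may hold the ranking. Much analysis detail may properly sit there. The choice of primary result belongs in the protocol, though, and a ranking in the SAP would leave this list still wrong.

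**Conclusion.** Wrong as written for the five predictors that are listed as outcomes. For the three results, designating one is a cheap improvement that should be made. The size is 5 of 8 items mislabelled and none of 3 results marked as the main one. The harm is selective reporting, greatest in the retrospective part; no stated error rate is breached.

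Two further readings go beyond the text. A reader might infer that testicular volume should be the one primary predictor, because the background calls it apparently the most predictive factor. That support is a single retrospective study of 31 patients, cautiously worded, and Objective 1 asks for parameters in the plural. A reader might also take the point to show that 30-40 adolescents are too few; nothing here bears on that.

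The conclusion rests on the wording of the protocol alone and needs no assumed retrieval rate, correlation or significance level. Preferring presence as the primary result rests on Objective 1.

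**What to change.** 1. In Study parameters, move testicular volume (with its Tanner fallback), testosterone, LH, FSH and age at TESE under a heading for candidate predictors. Keep all five.
2. Name presence of spermatozoa among those who undergo TESE as the single primary result of Part 1, in line with Objective 1.
3. Make number of straws and sperm quality secondary, and state that quality is described only where sperm are found.
4. Reword the Part 1 question in Study design so that yield and Objective 1 point to the same result.
5. In Statistical analysis, analyse the yes/no primary result with a binary-outcome model (logistic regression, penalised if events are few) and report estimates with 95% confidence intervals.

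No patients, visits or measurements are added. Step 5 changes the analysis as well as the labels. The price is that straws and quality lose primary status, although yield is part of the protocol's own question; both are still reported.
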